#### 4.5.2. PK Variables

Blood (plasma) samples for PK analysis will be collected according to the schedule of assessment (**Table 3**). Plasma concentrations of SLV213 will be quantitated using validated assays and study drug concentration data will be transferred to SDCC (Emmes) from the bioanalytical lab, KCAS, for reporting and PK analysis. PK parameters to be estimated for single dose and multiple dose plasma samples are described in **Section 10**.

## 5. SAMPLE SIZE CONSIDERATIONS

The sample size chosen of a total of 36 participants (12 per cohort: 8 to receive active drug and 4 placebo) is considered to be sufficient for evaluation of safety, tolerability and PK data for this study; the sample size was not based on statistical power considerations ([Table 4](#)).

Participants will be replaced if they withdraw or are withdrawn prior to Day 1 of treatment. The replacement participant would receive the same treatment that the participant would have received.

Participants who withdraw or are withdrawn from this study after receiving at least one dose of study product and prior to Day 9 for reasons not related to TEAEs or study drug intolerance may be replaced, at the recommendation of the Site PI and concurrence by the DMID MO, with a participant who will receive the same treatment as the withdrawn participant, and an effort will be made to also be of the same gender as the participant who is replaced. The SDCC must be contacted prior to enrolling any replacement participants.

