4. STUDY DESIGN

4.1 Overall Design

This Phase 1 double blind, placebo-controlled study will consist of three sequential inpatient cohorts of 12 healthy participants each (8 SLV213 and 4 placebo), at doses of 400 mg Q12h, 600 mg Q12h, and 800 mg Q12h for 7 days administered PO. After each cohort has been dosed, a SRC will evaluate the safety of the regimen to Day 15 before proceeding to dose the next cohort. The study will be carried out in the US at a single clinical trial unit (CTU). Subjects who have consented to participate in the study, as evidenced by signing the informed consent form (ICF), will undergo study procedures to determine their eligibility to receive study drug.

Upon meeting Inclusion/Exclusion criteria, participants will begin dosing with SLV213 or placebo per their allotted cohort. Participants will take their study drug prior to morning and evening meals. AEs will be noted and graded per the protocol Toxicity Grading Tables (See [Appendix A](#)). Visit assessments are shown in the schedule of events ([Section 1.2](#)) and [Section 8.1](#) and [Section 8.3](#).

Participants will be assigned to receive their treatment according to the randomization carried out by the clinical site. For each dosing cohort, randomized participants will be assigned a unique number. Participants will be replaced if they withdraw or are withdrawn prior to Day 1 of treatment. The replacement participant would receive the same treatment that the participant being replaced would have received. A unique number will be the only participant identifier used on all sample collections and return of results. The site's unblinded pharmacist or qualified designee will provide each participant's study drug to blinded clinical staff at the participating site. All doses will be administered to the participant at the site by delegated staff under the supervision of licensed clinical staff authorized to administer study drug (PI, or sub-investigator or licensed clinicians listed on Form FDA 1572). The investigational drug blind is maintained by the dispensing pharmacist through a randomization schedule.

A schematic of the study design is presented in [Section 1.3](#). The schedule of activities is in [Section 1.2](#).

Full details about timing of analyses are found in [Section 9.3.2](#).

Details of the SMC oversight are found in [Section 10.1.6](#).

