8.5.9 Adverse Events of Special Interest (AESI)

Definition of AESI

An AESI (serious or non-serious) is one of scientific and medical concern specific to the compound or program, for which ongoing monitoring and rapid communication by the investigator to the Sponsor may be appropriate. Such clinically significant events may require further investigation in order to characterize and understand them and will be collected as AESIs, discussed by the SMC, and expanded narratives of each written as indicated.

Protocol-defined AESIs are:

- All clinically significant cardiovascular Grade 3 or higher AEs including symptomatic cardiac arrhythmias and ECG abnormalities
- All clinically significant Grade 3 or higher gastrointestinal AEs
- Hepatic toxicity assessed by severe (Grade 3 or higher) based on values of liver function tests (LFTs)

All AESIs will be collected through study Day 28 and will be included in the safety analysis.

All AESIs are assessed for severity and relatedness to investigational product, recorded, and followed as described above under AEs and SAEs.

Reporting of AESI

All AESIs, whether serious or non-serious, also require additional reporting to the DMID PVG within 24 hours of site awareness for serious AESI or within 72 hours of site awareness for non-serious AESI. AESIs are reported on the appropriate CRF with additional reporting to DMID PVG using the protocol-approved SAE form. Submit AESI as follows:

DMID Pharmacovigilance Group
Clinical Research Operations and Management Support (CROMS)
[name]
[name]
SAE Hot Line: [name] (US) or [name] (outside US)
SAE [contact] (US) or [name] (outside US)
SAE Email Address: [contact]

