### 3. STUDY OBJECTIVES AND ENDPOINTS

OBJECTIVE	ENDPOINTS (OUTCOME MEASURES)
Primary To evaluate the safety and tolerability of multiple ascending doses SLV213 for 7 days in healthy participants.	Primary Safety: Type, incidence, severity, and relatedness to study drug of all treatment-emergent systemic, laboratory and electrocardiographic (ECG) adverse events (AEs) and serious adverse events (SAEs) in each treatment cohort from the first dose (Day 1) through the last visit (Day 28 ± 2 days). Tolerability: Summarized by dose cohort and include: 
 
• Number (and percentage) of participants who:           
 
1) Terminate early or are withdrawn due to treatment-emergent AEs assessed as related to intake of study medication.
 
2) Have at least 1 treatment-emergent adverse event (TEAE), total and per dose level.
 
3) Meet Grade 3 abnormal criteria for safety laboratory tests at least once post-dose.
 
4) Meet Grade 3 abnormal criteria for vital sign measurements at least once post-dose.
 
5) Meet Grade 3 criteria for safety electrocardiogram (ECG) parameters at least once post-dose.
 
 
 
• Proportion of oral medication doses completed.
 

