#### 4.4.3. Method of Assigning Participants to Treatment Groups (Randomization)

Participants in each cohort will be randomized 2:1 to drug versus placebo before dosing on Day 1 and receive assigned treatment at each dose.

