## 12.2.2 Displays of Adverse Events

Adverse events will be graded per FDA Guidance (<https://www.fda.gov/media/73679/download>) unless otherwise specified.

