Potassium increase – mmol/L	5.1 – 5.2	5.3 – 5.4	5.5 – 5.6	> 5.6
Potassium increase – mmol/L	3.5 – 3.6	3.3 – 3.4	3.1 – 3.2	< 3.1
Carbon Dioxide increase – mEq/L	32.1 – 36.0	36.1 – 40.0	> 40.0	Intervention indicated
Carbon Dioxide decrease – mEq/L	17.0 – 21.9	14.0 – 16.9	< 14.0	Metabolic acidosis Invention indicated
Calcium increase – mg/dL	10.5 – 11.0	11.1 – 11.5	11.6 – 12.0	> 12.0
Calcium decrease – mg/dL	8.0 – 8.4	7.5 – 7.9	7.0 – 7.4	< 7.0
Creatinine increase – mg/dL	1.50 – 1.79	1.80 – 2.00	2.01 – 2.50	> 2.50
BUN increase – mg/dL	23 – 26	27 – 31	> 31	Requires dialysis
Glucose (fasting) increase – mg/dL	100 - 110	111 - 125	>125	Insulin requirements or hyperosmolar coma
Glucose (fasting) decrease – mg/dL	65 – 69	55 – 64	45 – 54	< 45
Total Protein decrease – g/dL	5.5 – 6.0	5.0 – 5.4	< 5.0	--
Albumin decrease – g/dL	2.8 – 3.1	2.5 – 2.7	< 2.5	--
Total Bilirubin increase – mg/dL, when LFT  normal	1.5 – 2.1	2.2 – 2.7	2.8 – 4.2	> 4.2
Total Bilirubin increase – mg/dL, when LFT  increased	1.5 – 1.6	1.7 – 2.1	2.2 – 2.4	> 2.4
Alanine Aminotransferase (SPGT/ALT) increase – U/L, female male	44 – 100 60 – 137	101 – 200 138 – 275	201 – 400 276 – 550	> 400 > 500
Aspartate Aminotransferase (SGOT/AST) increase – U/L, female male	38 – 87 55 – 125	88 – 175 126 – 250	176 – 350 251 – 500	> 350 > 500
Alkaline Phosphatase (ALP) increase – U/L, female male	114 – 208 141 – 258	209 – 312 259 – 387	313 – 1040 388 – 1290	> 1040 > 1290
Amylase increase – U/L	110 – 150	151 – 200	201 – 500	> 500
Lipase increase – U/L	66 – 90	91 – 201	121 – 300	> 300
Magnesium decrease – mg/dL	1.30 – 1.50	1.10 – 1.29	0.90 – 1.09	< 0.90
Phosphorus (inorganic) decrease – mg/dL	2.3-2.5	2.0 – 2.2	1.6 – 1.9	< 1.6
Hematology				
Hemoglobin decrease – g/dL, female male	11.0 – 12.0 12.5 – 13.5	9.5 – 10.9 10.5 – 12.4	8.0 – 9.4 8.5 – 10.4	< 8.0 < 8.5
Hemoglobin decrease – g/dL,	Any decrease – 1.5	1.6 – 2.0	2.1 – 5.0	> 5.0

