## 14.2 Tolerability Data

**Table 14: Tolerability by Treatment Group, Safety Population**

Participants who:	400 mg SLV213 (N=X)		Placebo (N=X)	
	n	%	n	%
Terminated early or withdrawn due to TEAE related to study product	x	xx	xx	xx
Have at least one TEAE				
Met Grade 3 abnormal criteria at least once post-dose for				
Safety laboratory tests				
VS measurements				
Safety ECG parameters				
Completed all oral medication doses				

Note: N = Number of participants in the Safety Population; n = Number of participants meeting each tolerability category criteria.

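### SAP Table 4 prints a 1:1 split against the 2:1 design, and SAP Table 8 gives two grades to lipase 121–201 U/L and to male ALT 501–550 U/L

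*SAP*

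**What the plan says.** **Sample size.** SAP section 5 states "The sample size chosen of a total of 36 participants (12 per cohort: 8 to receive active drug and 4 placebo", and refers to Table 4 in the same sentence. Protocol section 4.1 describes "three sequential inpatient cohorts of 12 healthy participants each (8 SLV213 and 4 placebo", and SAP section 4.1 says the same. SAP section 4.4.3 gives the ratio: "Participants in each cohort will be randomized 2:1 to drug versus placebo before dosing on Day 1". Table 4, placed under report section 9.7.1, prints 6 for each of the three dose groups and 18 for placebo.

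**Laboratory grading.** SAP section 9 names the FDA healthy-volunteer toxicity scale and provides Table 8 as the grading scale for laboratory results. The heading note in Appendix 1, section 12.2.2, makes that FDA scale apply "unless otherwise specified". Table 8 prints these limits (U/L):

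| Test | Grade 1 | Grade 2 | Grade 3 | Grade 4 |
|---|---|---|---|---|
| Amylase | 110–150 | 151–200 | 201–500 | >500 |
| Lipase | 66–90 | 91–201 | 121–300 | >300 |
| ALT, female | 44–100 | 101–200 | 201–400 | >400 |
| ALT, male | 60–137 | 138–275 | 276–550 | >500 |
| AST, female | 38–87 | 88–175 | 176–350 | >350 |
| AST, male | 55–125 | 126–250 | 251–500 | >500 |

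**Where the grades are used.** SAP section 3 lists among the primary tolerability endpoints the number of participants who "Meet Grade 3 abnormal criteria for safety laboratory tests at least once post-dose". Table 14 reports it under "Met Grade 3 abnormal criteria at least once post-dose for". Table 33 reports chemistry results by maximum severity.

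**The concern.** These are two independent errors in different tables.

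Table 4 contradicts the sentence that cites it. It cannot be read as actual enrolment, because it still carries counts for the two dose groups it labels as not enrolled. The result shells use N=X, so no percentage or interval depends on it. Left as it is, the report would misstate the planned arms.

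The Table 8 overlaps affect how data are classified. A lipase of 121–201 enters the primary Grade 3 laboratory count if read from one cell and stays out if read from the other. A male ALT of 501–550 changes its severity row in Table 33. It may also leave the Table 14 row, because that row says Grade 3 only, whereas the protocol elsewhere uses an open-ended form, as in "Hepatic toxicity assessed by severe (Grade 3 or higher) based on values of liver function tests (LFTs".

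Two shell lists also disagree with the grading table. Table 8 has a row for "Glucose (fasting) decrease – mg/dL", and SAP section 9.6 requires tests graded in both directions to be summarized by direction, yet the Table 33 list of parameters that may decrease omits glucose. Table 34 has the reverse fault: it lists hemoglobin increase, which Table 8 does not grade.

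**Working it through.** **Table 4**

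- Plan's own figure: 6 + 6 + 6 + 18 = 36. The total reproduces.
- Stated design: 3 cohorts × 8 = 24 active; 3 cohorts × 4 = 12 placebo; 24 + 12 = 36.
- Splits of 36: 2:1 gives 24/3 = 8 per dose and 12 placebo; 1:1 gives 18/3 = 6 per dose and 18 placebo; 3:1 gives 27/3 = 9 per dose and 9 placebo.
- Of these, only 1:1 reproduces the printed rows, and neither document states 1:1.
- Differences: active 18 printed against 24; placebo 18 against 12; Cohort 1 active 6 against 8.

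**Table 8, overlaps**

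- Lipase: Grade 2 ends at 201 and Grade 3 starts at 121. Doubly graded integers: 201 − 121 + 1 = 81. The Grade 2 band holds 201 − 91 + 1 = 111 integers and the Grade 3 band 300 − 121 + 1 = 180, so the overlap is 81/111 = 73% of the first and 81/180 = 45% of the second.
- Male ALT: Grade 3 ends at 550 and Grade 4 starts above 500. Doubly graded integers: 550 − 501 + 1 = 50. The Grade 3 band holds 550 − 276 + 1 = 275, so the overlap is 50/275 = 18%.
- All 17 high-direction rows with four numeric grades were checked for adjacency, counting female and male rows separately. Only these two boundaries fail.

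**Which cells break the table's own pattern**

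- Lipase limit divided by amylase limit: 66/110 = 0.600; 90/150 = 0.600; 201/200 = 1.005; 300/500 = 0.600. Only the Grade 2 upper limit departs. 0.6 × 200 = 120, which would also meet the printed Grade 3 start of 121.
- Grade 3 upper limit divided by Grade 2 upper limit, in the order ALT female, ALT male, AST female, AST male: 400/200, 550/275, 350/175, 500/250, all 2.0.
- Grade 4 threshold divided by Grade 2 upper limit, same order: 400/200 = 2.0; 500/275 = 1.82; 350/175 = 2.0; 500/250 = 2.0. Only male ALT departs.

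This shows which cells are out of line. It does not establish the intended limits.

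**Does any other text assign a single grade?**

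- The deferral in section 12.2.2 gives way where the SAP specifies something else, and Table 8 does specify limits.
- Protocol Appendix A links to the FDA scale; its printed supplemental tables contain neither lipase nor ALT.
- The Table 33 maximum-severity rule covers several graded events at one time point, not one value that fits two grades. Table 14 has no such rule.

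**Scale of one reclassification.** SAP section 6.2 reports four replacement participants but not their arms. If 8 to 12 active participants are analysed (an assumption), one participant moves the Table 14 row by 1/12 = 8 to 1/8 = 13 percentage points.

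**The case against.** The strongest reply is that a governing source exists. SAP section 9 and protocol section 8.5.4 adopt the FDA scale, so Table 8 may be a faulty transcription and the grade not truly undefined. That stands as far as it goes, and it is why the remedy is reconciliation with that scale. But Table 8 is the scale the SAP supplies for laboratory results, and an analyst following it as printed meets two grades for one value.

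It is also fair that Table 4 is contradicted by several correct statements in the same SAP and changes no result. On that part the point is a correction to the report and no more.

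The ALT overlap carries less weight than the lipase one. Both readings are Grade 3 or higher, so the hepatic special-interest criterion is unaffected. Male Grade 1 starts at 60, so a value above 500 also exceeds five times any upper limit of normal below 60, a level named in the hepatic cohort halting rule (protocol 7.1.1). SAP section 6.2 describes the halt through two moderate allergic reactions and mentions no liver event. SAP section 4.1, however, speaks of multiple halting rules, so absence of such a value cannot be inferred. The cell also differs by a single digit from the one the pattern suggests and should be confirmed on the signed page.

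The overlap percentages are widths of grading bands, not probabilities that a count changes. Low glucose would still appear in the abnormal-results listing even if missing from Table 33.

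Finally, the shell mismatches go beyond the two named above. Table 36 lists urine bilirubin, which SAP section 4.5.1 says is not graded, and Table 37 lists low diastolic pressure, which Table 7 does not grade. That is correct and belongs in the same clean-up.

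**Conclusion.** The concern holds. Table 4 misstates the planned arms: 18 active and 18 placebo against 24 and 12, with no effect on any analysis denominator. Table 8 assigns two grades to 81 integer lipase values and 50 integer male ALT values. The lipase overlap by itself makes the primary Grade 3 laboratory count contradictory as written. The ALT overlap alters Table 33, and alters Table 14 only if its Grade 3 row excludes Grade 4, which the plan does not say.

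No change to an observed result is claimed, since the documents do not report whether a value fell in either range. The integer counts assume results reported in whole U/L. The pattern-based limits are inference.

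**What to change.** Make the changes by SAP addendum if final data lock has not occurred (SAP section 15); otherwise record them as a stated correction in the study report (SAP section 1).

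1. Set Table 4 to 8, 8, 8 and 12, and note that Cohort 1 was planned as 8 active and 4 placebo before the four replacements.
2. Reconcile the lipase Grade 2 upper limit and the male ALT Grade 4 threshold with the cited FDA scale, so that every value has one grade. The table's pattern points to 120 and 550; neither should be adopted without confirmation against that source.
3. Add fasting glucose decrease to the Table 33 list. Remove hemoglobin increase from Table 34 or give it a grade. Treat urine bilirubin in Table 36 and low diastolic pressure in Table 37 in the same way.
4. State whether the Grade 3 rows of Table 14 include Grade 4, leaving the protocol endpoint otherwise unchanged.

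Proofread at the same time, with no effect claimed: the shared 102.1 °F fever boundary, the low-potassium row labelled as an increase, the urine white-cell Grade 1 range starting at 0, the unit of the ventricular pause, and a QTcF increase of exactly 60 msec, which falls in no grade by its change limits.

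The cost of items 1 to 4 is four cells in Table 4, two in Table 8, four list entries and one sentence. They need no new data and no protocol change.

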## 6. GENERAL STATISTICAL CONSIDERATIONS

### 6.1. General Principles

All continuous variables will be summarized using the following descriptive statistics: n (non-missing sample size), mean, standard deviation, median, maximum, and minimum. The frequency and percentages (based on analysis population sample size, unless otherwise stated) of observed levels will be reported for all categorical measures. In general, all data will be listed, sorted by treatment group, participant, parameter, and time point as applicable.

The Safety Population will be the primary population used for summaries of safety endpoints. The PK Analysis Population will be used for summaries of PK endpoints. Analyses of primary and secondary endpoints will be done for each dose of SLV213 and compared with a placebo group.

### 6.2. Timing of Analyses

The primary clinical database for this study will consist of safety data including unsolicited events, and abnormal laboratory values, as well as baseline/demographic data. Once the last participant has completed the final visit, the primary clinical database will be cleaned, monitored, and locked. After clinical database lock and receipt of secondary endpoint data, a set of topline tables will be generated, including summaries of clinical safety and secondary PK data. The topline report will be made available to the study team for planning subsequent trials and may be presented in a public forum or used for publication in collaboration with the lead PI. These analyses will be considered final and will be included in the Clinical Study Report (CSR).

#### Interim Analysis

Blinded safety and tolerability data will be periodically reviewed by DMID and the site PI or authorized study clinician (listed on FDA Form 1572) to assess whether rules for halting progression to the next study cohort have been met. An *ad hoc* SMC meeting will review safety data if halting criteria have been met. The SMC will receive data in aggregate. The SMC may request to receive data by study product vs. placebo in a closed session. The SMC may also request that the blind be broken for individual participants, as needed, to assess safety issues. The SMC will be asked to recommend early termination or modification only when there is clear and substantial evidence of a treatment difference. More details about the interim analyses are described below, as well as in a separate guidance document for the SMC.

#### Interim Safety Analyses

Interim safety analysis is not planned. Safety data may be summarized for *ad hoc* review as requested by the SMC. Top level safety parameters will be assessed between cohorts as needed.

After one participant experienced a moderate allergic reaction, further dosing was discontinued in four participants. As a result, four replacement participants were added at the advice of the SMC. One of these replacement participants also had a moderate allergic reaction to the study product. After meeting a halting rule criterion, the study was halted, and the SMC reviewed data of the two participants who reported a moderate allergic reaction. Under the advisement of the SMC, the study will not proceed with Cohort 2 and Cohort 3.

## **Interim Pharmacokinetics, Pharmacodynamic, Microbiological Activity, or Efficacy Review**

An interim PK and pharmacodynamics (PD) analysis is not planned. If concentration versus time or PK data are available, top-level concentration versus time curves or PK parameters will be assessed between cohorts as needed.

### **Final Analyses**

Final analysis will be completed after study completion and database lock. No formal study data will be provided prior to this final analysis.

## **6.3. Analysis Populations**

### **6.3.1. Full Analysis Population**

The Full Analysis population will include all randomized participants, including replacement participants, and analyzed according to the treatment as randomized. This population is analogous to an intent-to-treat population.

### **6.3.2. Modified Intention-to-Treat (mITT) Population**

The mITT population will include all randomized participants, including replacement participants, who meet eligibility criteria and receive at least one dose of any study treatment. Participants will be excluded from the mITT population, if they fail to meet eligibility criteria or if they do not receive any study treatment. Analysis will be performed according to the treatment as randomized.

### **6.3.3. Safety Population**

The Safety population will include all randomized participants, including replacement participants, who received at least one dose of any study treatment, and analysis will be performed according to the treatment actually received.

### **6.3.4. Pharmacokinetics (PK) Population**

The PK population will include all randomized participants, including replacement participants, who received at least one dose of study treatment and have at least one quantifiable post-dosing plasma concentration to use for the PK analysis.

